3.9.3.3. Electrocardiograms

Descriptive statistics for ECG parameters (heart rate, PR interval, RR interval, QRS interval, QT interval, and QTc interval) at baseline and change from baseline values at each assessment timepoint and at the end of the double-blind treatment period will be presented by treatment group. QTc interval will be calculated using both Bazett ($QTcB = QT/(RR)^{1/2}$) and Fridericia ($QTcF = QT/(RR)^{1/3}$) corrections; if RR is not available, it will be replaced with 60/HR in the correction formula.

Electrocardiogram parameter values are considered PCS if they meet or exceed the higher-limit PCS criteria listed in Table 7. The number and percentage of subjects with PCS post-baseline ECG values will be tabulated by treatment group. The percentages will be calculated relative to the number of subjects with normal baseline values and at least 1 post-baseline assessment. The numerator is the total number of subjects with normal baseline values and at least 1 PCS post-baseline value. A supportive tabular display of subjects with PCS post-baseline values will be provided, including the subject ID number, study center number, baseline, all post-baseline (including non-PCS) values, and change from baseline.

Table 7: Criteria for Potentially Clinically Significant (PCS) QTcB and QTcF

Parameter	Criteria
QTcB and QTcF	>450 to ≤ 480 msec
	>480 to ≤ 500 msec
	>500 msec
	Change from baseline >30 to ≤ 60 msec
	Change from baseline >60 msec

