#### **7.2.5. Exclusion Criteria Based on Laboratory Assessments at Screening**

20. Subject has any of the following lab results at screening:

- Hemoglobin A1c (HbA1c)  $\geq 6.0\%$
- Dyslipidemia, defined for this study as total fasting cholesterol >280 mg/dL or fasting triglycerides >500 mg/dL
- Aspartate aminotransferase (AST) or alanine aminotransferase (ALT) value  $\geq 2$  times the upper limit of the laboratory normal reference range
- Absolute neutrophil count  $\leq 1.5 \times 10^3 \mu\text{L}$
- Platelet count  $\leq 75 \times 10^3 \mu\text{L}$
- Serum creatinine >2.5 mg/dL
- Positive pregnancy test result

21. Positive serology test for hepatitis B surface antigen, hepatitis C antibody (confirmed by RNA testing), or human immunodeficiency virus (HIV) antibody at screening

22. Clinically significant ECG abnormality at Visit 1 or baseline Visit 2

23. QT interval >450 msec for men and >470 msec for women, as corrected by the Fridericia formula (QTcF), observed at Visit 1 or baseline Visit 2

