3.9.3.2. Weight and Body Mass Index

Weight (kg), BMI (kg/m²) and waist circumference (baseline and change from baseline) will be summarized by treatment group. Height (cm) will be measured at the screening visit and this value will be used for the calculation of the BMI. All weight, BMI and waist circumference data will be listed.

Number and percentage of subjects with weight change values considered as PCS occurring at any post-baseline visit will be summarized by treatment group. Criteria for PCS are presented below. The percentages will be calculated relative to the number of subjects in the Safety Population with at least one post-baseline value. A supportive listing will be provided for subjects with PCS values.

Table 6: Criteria for Potentially Clinically Significant (PCS) Changes from Baseline in Body Weight

Parameter	Criteria
Body Weight	Decrease from Baseline $\geq 7\%$ Increase from Baseline $\geq 7\%$

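### The QTc outlier table counts only subjects with an undefined 'normal' baseline, so some eligible subjects who pass 500 msec or change by more than 60 msec can be missing from its percentages

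*SAP*

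**What the plan says.** SAP 3.9.3.3 (Electrocardiograms) tabulates potentially clinically significant (PCS) QTc values by arm. The denominator rule is "The percentages will be calculated relative to the number of subjects with normal baseline values and at least 1 post-baseline assessment". The numerator rule matches it: "The numerator is the total number of subjects with normal baseline values and at least 1 PCS post-baseline value". No row of Table 7 is exempt. The rows start at "QTcB and QTcF >450 to ≤ 480 msec", with no distinction by sex, and run through >480 to ≤500 and >500 msec to two change rows, the larger being "Change from baseline >60 msec". Both corrections are tabulated: "QTc interval will be calculated using both Bazett" and Fridericia corrections. The section gives no numeric meaning for a normal baseline.

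Entry is governed by Protocol 7.2.5. Exclusion 23 removes subjects with "QT interval >450 msec for men and >470 msec for women, as corrected by the Fridericia formula (QTcF"). Exclusion 22 removes those with a "Clinically significant ECG abnormality at Visit 1 or baseline Visit 2", which is a judgment without a number. Neither states a QTcB limit.

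Three other places bear on the point:

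- Protocol 14.6 describes the PCS summary without any baseline restriction. SAP section 5 declares only the added region factor as a change.
- For weight change, SAP 3.9.3.2 uses no baseline restriction: "The percentages will be calculated relative to the number of subjects in the Safety Population with at least one post-baseline value".
- For laboratory values (SAP 3.9.2) and vital signs (SAP 3.9.3.1), the SAP does restrict by baseline, but to subjects who did not already meet the PCS criteria.

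**The concern.** A baseline restriction makes sense when a row counts new entry into a band: someone already in the band cannot newly enter it. SAP 3.9.3.3 goes further. One baseline test removes a subject from all rows, including rows the subject was nowhere near at baseline. A subject who starts a little above 450 msec and ends above 500 msec has had the event that the >500 row exists to show. In a change row each subject serves as their own reference, so an abnormal starting value is no reason for removal.

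The entry rules let such subjects in, and they start closest to 500 msec. At stake are the rates by arm in the most serious QTc categories, where events are few and one omitted subject can alter the count materially.

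**Working it through.** There is no stated figure to reproduce. The check applies the SAP rule to baselines that entry permits, and then shows how the percentage responds.

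**Step 1. Apply the rule.** Two fixed-limit readings of normal are tried: A, ≤450 msec for everyone (the floor of Table 7); B, the QTcF entry limits, ≤450 for men and ≤470 for women. The cases are illustrative.

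| Measure, sex | Baseline to post-baseline (change), msec | Table 7 rows met | Counted under A | Counted under B |
|---|---|---|---|---|
| QTcF, woman | 460 to 505 (+45) | >500; change >30 to ≤60 | no | yes |
| QTcF, woman | 465 to 530 (+65) | >500; change >60 | no | yes |
| QTcF, man | 450 to 511 (+61) | >500; change >60 | yes | yes |
| QTcB, man | 475 to 540 (+65) | >500; change >60 | no | no |
| QTcB, woman | 485 to 550 (+65) | >500; change >60 | no | no |

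The QTcF cases all satisfy exclusion 23. The QTcF gap exists under A and closes under B. The QTcB gap exists under both.

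**Step 2. Are those QTcB baselines open to eligible subjects?** The SAP formulas are QTcB = QT/RR^(1/2) and QTcF = QT/RR^(1/3), with RR = 60/HR. Dividing one by the other gives QTcB = QTcF × RR^(-1/6). Heart rates below are assumed.

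| Heart rate (bpm) | Factor | QTcB when QTcF = 450 | QTcB when QTcF = 470 | QTcF at which QTcB = 450 |
|---|---|---|---|---|
| 60 | 1.000 | 450.0 | 470.0 | 450.0 |
| 70 | 1.026 | 461.7 | 482.2 | 438.6 |
| 80 | 1.049 | 472.1 | 493.1 | 428.9 |
| 90 | 1.070 | 481.5 | 502.9 | 420.6 |

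The man with QTcB 475 has QTcF 475/1.0699 = 444.0 at 90 bpm, inside the limit of 450. The woman with QTcB 485 has QTcF 485/1.0491 = 462.3 at 80 bpm, inside 470. Both can enter on exclusion 23. At 90 bpm a woman at the QTcF limit already has QTcB above 500, which matters for the fix.

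**Step 3. Effect on a reported percentage.** Let N be the subjects in an arm with a baseline and a post-baseline ECG, k those without a normal baseline, a the events among the N − k, and b the events among the k.

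- SAP rule: a/(N − k).
- All subjects: (a + b)/N. This is also the fixed >500 row if nobody starts above 500.

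Take N = 130 (planned per arm, SAP section 2), and assume k from 1 to 26 (about 1% to 20%) and a = 1.

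- SAP rule: 1/129 = 0.78% up to 1/104 = 0.96%.
- All subjects, b = 1: 2/130 = 1.54%.
- All subjects, b = 2 (needs k of at least 2): 3/130 = 2.31%.
- All subjects, b = 0: 1/130 = 0.77%, marginally below the SAP figure.

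The number of subjects counted can only fall under the SAP rule. The percentage is understated when b/k exceeds a/(N − k), that is, when the omitted subjects have the higher event rate. That is plausible for >500 msec, since they start nearer to it. For the change rows the direction is open.

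**The case against.** **The QTcF example depends on an undefined word.** If normal means the entry limits, women at 451-470 msec are counted. This stands. A reader might infer that these women are certainly dropped; the SAP does not say enough for that. It does not help QTcB, which has no numeric entry limit, although exclusion 22 may remove some such subjects by judgment.

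**Normal might mean not already meeting that row's criterion,** as in the laboratory and vital-sign rules. A baseline of 455 msec would then stay in the >500 row, and no baseline could meet a change criterion. This reading is possible, but SAP 3.9.3.3 uses a different word from those sections and states one rule for the whole table. If it was intended, writing it down gets most of the way to the fix.

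**Restricting by baseline is this SAP's usual practice,** and the weight rule is an imperfect comparator because weight has only percentage-change criteria. Both remarks are fair. They support a baseline condition for the absolute bands, set band by band. They do not support one condition for every row.

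**The subjects are not lost from safety reporting.** This stands. A reader might infer that they vanish, but the supportive display gives baseline, all post-baseline values and change for subjects with PCS values, with no baseline restriction in its wording. The descriptive change statistics have none either. What is missing is a rate by arm: a display gives none, and means dilute outliers.

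**A reader might also infer a bias towards ALKS 3831.** The documents do not support that. The condition rests on a value obtained before the first dose and applies alike in all arms.

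**Conclusion.** The point holds in a conditional form. The text limits numerator and denominator of every Table 7 row to an undefined normal baseline. Under either fixed-limit reading, eligible subjects with raised baseline QTcB can be left out of every percentage. For QTcF the gap is women at 451-470 msec, and only if normal means ≤450 msec.

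The consequence is that rates of >500 msec and of change >60 msec can be understated in an arm. The size cannot be derived: the documents give neither a baseline QTc distribution nor event rates. Assumed means and SDs would show only how many subjects start above 450 msec, not how many events the table misses, and a QTcB share computed without regard to the QTcF entry limits would not describe the enrolled population. The figures in step 3 show the mechanism under stated assumptions and are not an estimate.

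This is a descriptive safety table and does not touch the primary analysis. Because the rule acts on the gravest rows and is cheap to change, it should be corrected before database lock and unblinding.

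**What to change.** In SAP 3.9.3.3, replace the single baseline condition with one for each type of row, applied separately to QTcB and QTcF:

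- **Two change-from-baseline rows:** all Safety Population subjects with a baseline and at least one post-baseline ECG.
- **Absolute bands (>450, >480, >500 msec):** subjects whose baseline is at or below that band's lower limit and who have at least one post-baseline ECG. Only subjects already above 500 msec at baseline then leave the >500 row.

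Use the same condition for numerator and denominator, and print the denominator beside each percentage. The word normal is then no longer needed. If it is kept anywhere in the section, give it a number for each correction and, if intended, for each sex.

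The cost is SAP wording and one table program. Data collection, eligibility and trial conduct are unchanged. The downside is that denominators will differ between rows and the stated rates may become slightly less favourable.

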3.9.4. Abnormal Movement Scales

Extra pyramidal symptoms (EPS) will be evaluated as AEs and also assessed by abnormal movement scales. Abnormal movement scales will include the following: Abnormal Involuntary Movement Scale (AIMS), Barnes Akathisia Rating Scale (BARS), and Simpson-Angus Scale (SAS).

For all abnormal movement scales, total scores and subscale scores will be summarized by treatment group at each visit for the absolute value and for changes from baseline.

Number and percentage of subjects meeting the criteria for treatment emergent Parkinsonism (SAS total score >3), for treatment emergent akathisia (BARS global clinical assessment of akathisia score ≥ 2), for treatment emergent dyskinesia (AIMS score ≥ 3 on any of the first 7

items, or a score ≥ 2 on two or more of any of the first 7 items) at any postbaseline visit will be summarized by treatment group.

A listing will be provided for every abnormal movement scale. Listing for treatment emergent EPS will be provided.

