3.9. Safety Analysis

3.9.1. Adverse Events

Adverse events will be coded by System Organ Class and Preferred Term using the Medical Dictionary for Regulatory Activities (MedDRA[®]) Version 19.0 or higher. The verbatim term will be included in the AE listings.

An AE (classified by preferred term) will be considered as treatment-emergent AE (TEAE) if the event is newly occurring or worsening on or after the date of first dose of study drug.

The number and percentage of subjects reporting TEAEs in each treatment group during the double-blind period will be presented by treatment group for the following categories:

- System organ class and preferred term
- Preferred terms in decreasing frequency, and also including the following subsets:
 - Experienced by $\geq 2\%$ of subjects in any treatment group
 - Experienced by $\geq 5\%$ of subjects in any treatment group and ≥ 2 times of placebo group
- System organ class, preferred term, and severity
- System organ class, preferred term for severe TEAEs
- System organ class, preferred term, and relationship
- System organ class, preferred term for drug-related TEAEs

If more than one AE is coded to the same preferred term for the same subject, the subject will be counted only once for that preferred term using the most severe and most related occurrence for the summarization by severity and by relationship to study drug.

In addition, the number and percentage of subjects reporting AEs during the Safety Follow-up Period will be tabulated by the system organ class, preferred term and treatment group.

The number and percentage of subjects who have serious adverse events (SAE) and AEs leading to premature discontinuation from the treatment will be summarized by preferred term and treatment group and will be sorted by decreasing frequency for ALKS 3831 group.

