3.9.3. Vital Signs, Body Weight, and ECG

3.9.3.1. Vital Signs

Descriptive statistics for vital signs and changes from baseline values at each scheduled time point will be presented by treatment group.

Vital sign values will be considered PCS if they meet both the observed-value criteria and the change-from-baseline criteria listed in Table 5. The number and percentage of subjects with PCS post-baseline values will be tabulated by treatment group. The percentages will be calculated relative to the number of subjects with available non-PCS baseline values and at least 1 post-baseline assessment. The numerator will be the total number of subjects with available non-PCS baseline values and at least 1 PCS post-baseline value. A supportive tabular display of subjects with PCS post-baseline values will be provided, including the subject ID number, baseline, and all post-baseline (including non-PCS) values.

All vital signs will be presented in the subject data listing.

Orthostatic hypotension (20/10) is defined as a fall in systolic blood pressure of at least 20 mmHg and a fall in the diastolic blood pressure of at least 10 mmHg upon standing from supine. Orthostatic hypotension (30) is defined as a fall in systolic blood pressure of at least 30 mm Hg upon standing from supine.

Orthostatic tachycardia is defined as a heart rate increase of 30 beats per minute (bpm) or more upon standing from supine, or over 120 bpm upon standing.

The number and percentage of subjects with orthostatic hypotension or orthostatic tachycardia occurring at any post-baseline visit will also be summarized by treatment group for the double-blind period.

Table 5: Criteria for Potentially Clinically Significant (PCS) Blood Pressure or Pulse Rate

Parameter	Criteria
Supine Systolic Blood Pressure	≤90 and decrease ≥20 mm Hg ≥180 and increase ≥20 mm Hg
Supine Diastolic Blood Pressure	≤50 and decrease ≥15 mm Hg ≥105 and increase ≥15 mm Hg
Supine Heart Rate	≤50 and decrease ≥15 bpm ≥120 and increase ≥15 bpm

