3.9.5. Columbia-Suicide Severity Rating Scale (C-SSRS)

The C-SSRS is a questionnaire used to measure the presence and intensity of suicidal ideation and behavior.

Suicidal behavior and suicidal ideation will be summarized descriptively. The number of subjects with suicidal ideation and suicidal behavior during the double-blind treatment period will be summarized by treatment group when applicable.

Supportive tabular display of subjects with all values will be provided, including subject ID number, treatment group, visit number, intensity of suicidal ideation, suicidal behavior type, and lethality of suicidal behavior.

Table 8: C-SSRS Categories for Analysis

Category	C-SSRS Item response is “YES”
Suicidal behavior	Preparatory acts or behavior Aborted attempt Interrupted attempt Actual attempt Complete suicide
Suicidal ideation	Wish to be dead Non-specific active suicidal thoughts Active suicidal ideation with any methods (not plan) without intent to act Active suicidal ideation with some intent to act, without specific plan Active suicidal ideation with specific plan and intent

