6.1. Analysis Visit Windows

Scheduled analysis visits are visits at scheduled timepoints as specified in the protocol ([Table 1 Schedule of Visits and Assessments](#)).

Scheduled analysis visits during the study period will be the same as the nominal visits collected in eCRF. There will be one valid value of assessment kept for each scheduled analysis visit in summary/analysis statistics.

Unscheduled visits are visits with data not collected on the scheduled time point. Unscheduled visits will not be used for by-visit summary/analysis statistics unless specified otherwise.

All unscheduled visits will be included as collected in eCRF in listings.

Visit Day is calculated as (visit date) – (date of the first dose of study drug) +1.

Last postbaseline values are defined as the last valid postbaseline values collected for each subject during the double-blind treatment period.

Any post-baseline values are defined as any valid values collected from scheduled visits if applicable.

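### SAP 3.9.4 counts treatment-emergent parkinsonism, akathisia and dyskinesia without requiring a negative baseline or limiting the count to the double-blind period

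*SAP*

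**What the plan says.** SAP 3.9.4 labels three outcomes as treatment emergent and defines each by a score. For the first it gives "Number and percentage of subjects meeting the criteria for treatment emergent Parkinsonism (SAS total score >3"). Akathisia is a BARS global score of 2 or more. Dyskinesia is an AIMS score of 3 or more on one of the first seven items, or of 2 or more on at least two of them. Subjects who meet a criterion "at any postbaseline visit will be summarized by treatment group". The section sets no condition on the baseline score and names no period.

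SAP 6.1 gives two timing definitions, one after the other. The first is: "Last postbaseline values are defined as the last valid postbaseline values collected for each subject during the double-blind treatment period". The second is: "Any post-baseline values are defined as any valid values collected from scheduled visits if applicable". Only the first names the double-blind period.

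Protocol Table 1 schedules the three scales predose on Day 1, at Visits 3 to 6, and at Visit 7 (Day 43). Subjects who enrol in the extension study do not need Visit 7. Protocol 8.1 allows any antipsychotic during the two-week follow-up.

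Protocol 14.6 says that subjects with shifts in AIMS, BARS and SAS will be summarised. SAP 5 lists one change from the protocol, the region factor in the efficacy models.

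**The concern.** An outcome called emergent should pick out subjects who became positive on study drug. This rule picks out subjects who were positive at any time after baseline. That adds two groups who do not belong:

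- subjects already over a cut-off on Day 1 who are over it again later;
- subjects first over a cut-off at Visit 7, two weeks after the end of treatment and possibly on a different antipsychotic.

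Both groups are possible under the protocol. Section 8.4.2 allows a washout of only 2 to 5 days, so movement symptoms from earlier treatment may remain on Day 1. The exclusions in Section 7.2.4 rest on clinical history, and no entry criterion uses a SAS, BARS or AIMS score.

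Safety and tolerability is the only secondary objective. Readers would take these percentages as the rates of new movement disorder on each treatment.

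**Working it through.** **1. The rule beside the SAP's other safety counts**

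| Measure | Baseline condition | Period |
|---|---|---|
| Laboratory PCS (SAP 3.9.2) | not PCS at baseline, and at least one later value | none stated, but no samples are scheduled at Visit 7 |
| Supine vital-sign PCS (3.9.3.1) | percentages taken "relative to the number of subjects with available non-PCS baseline values" | none stated |
| Orthostatic events (3.9.3.1) | none stated | "occurring at any post-baseline visit will also be summarized by treatment group for the double-blind period" |
| ECG PCS (3.9.3.3) | normal at baseline | none stated |
| C-SSRS (3.9.5) | none stated | "suicidal ideation and suicidal behavior during the double-blind treatment period will be summarized by treatment group when applicable" |
| Adverse events (3.9.1) | new or worse after first dose | double-blind tables, and separately "subjects reporting AEs during the Safety Follow-up Period will be tabulated by the system organ class, preferred term and treatment group" |
| Movement scales (3.9.4) | none stated | none stated |

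Of these rows, only the movement-scale count has neither condition. Visit 7 is a scheduled visit in Protocol Table 1, so the SAP 6.1 definition of any post-baseline value admits it.

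**2. Possible size**

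The plan states no figure to reproduce. The only input from the documents is n = 130 per arm (SAP 2). All other inputs are assumptions:

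- p0, share positive at baseline: 0, 0.05 or 0.15
- s, share of those positive again later: 0.5 to 1.0
- p, true emergent rate among baseline negatives: 0.06 in one arm and 0.03 in the other
- v, share attending Visit 7: 0.3 to 1.0 (1.0 is a ceiling at which nobody enters the extension)
- q, share first positive at Visit 7: 0.02 to 0.05

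*Baseline positives.* Subjects wrongly labelled = n × p0 × s.

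- p0 = 0: 0
- p0 = 0.05: 130 × 0.05 × 0.5 = 3.25, up to 130 × 0.05 × 1.0 = 6.5
- p0 = 0.15: 130 × 0.15 × 0.5 = 9.75, up to 130 × 0.15 × 1.0 = 19.5

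Reported rate = p0 × s + (1 − p0) × p, with p0 and s the same in both arms:

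| p0 | s | Arm with p = 6% | Arm with p = 3% | Difference | Ratio |
|---|---|---|---|---|---|
| 0 | – | 6.00% | 3.00% | 3.00 | 2.00 |
| 0.05 | 0.5 | 2.5 + 5.7 = 8.20% | 2.5 + 2.85 = 5.35% | 2.85 | 1.53 |
| 0.05 | 1.0 | 5.0 + 5.7 = 10.70% | 5.0 + 2.85 = 7.85% | 2.85 | 1.36 |
| 0.15 | 0.5 | 7.5 + 5.1 = 12.60% | 7.5 + 2.55 = 10.05% | 2.55 | 1.25 |
| 0.15 | 1.0 | 15.0 + 5.1 = 20.10% | 15.0 + 2.55 = 17.55% | 2.55 | 1.15 |

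The percentages rise by 2.20 to 4.85 points at p0 = 0.05 and by 6.60 to 14.55 points at p0 = 0.15. The difference shrinks only by the factor (1 − p0).

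*Chance imbalance at baseline.* One SD of the between-arm difference in baseline positives is √(2 × p0 × (1 − p0)/130). This is 2.70 points at p0 = 0.05 and 4.43 points at p0 = 0.15. It reaches the table multiplied by s, and it is random error, not bias.

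*Visit 7 alone (p0 = 0).* Added rate = (1 − p) × v × q.

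- Smallest: 0.94 × 0.3 × 0.02 = 0.56 points, or 0.73 subjects per 130
- Largest: 0.97 × 1.0 × 0.05 = 4.85 points, or 6.31 subjects per 130

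With equal v and q in both arms, the difference moves from 3.00 to between 2.98 and 2.85 points.

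**The case against.** The strongest reply is that the label already carries the condition. SAP 3.9.1 defines treatment-emergent adverse events as new or worse after first dose, and SAP 3.9.4 plans a listing of emergent cases apart from the listing of each scale. A programmer might therefore require a negative baseline without being told to. Programming specifications and mock tables are separate documents and may contain the rule. That is possible, but the 3.9.1 definition is written for adverse events, and the criteria in 3.9.4 are plain cut-offs. The SAP writes the baseline condition out for laboratory values, supine vital signs and ECG, so leaving it out here is not harmless.

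The reply also notes that the table is descriptive and that other outputs limit the harm: scores and changes from baseline by visit, movement-related adverse events, and full listings. This stands. Those outputs do not give a count of new cases, however.

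A reader might infer several stronger points that the documents do not support:

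- *Every Day 1 positive is counted.* Day 1 predose is baseline, so the subject must be positive again at a later visit.
- *There is no denominator.* SAP 3.2.1 makes the Safety Population the default. What is missing is a denominator of subjects at risk.
- *The protocol's shift summary was silently dropped.* This is arguable. The SAP's laboratory shift tables are lists of threshold crossings, and the 3.9.4 counts could be meant as the same thing for the movement scales.
- *Unscheduled ratings prompted by complaints (Protocol 8.3.9.3.1) distort the count.* SAP 6.1 refers to scheduled visits, with a qualifier. SAP 7 admits unscheduled values only for PCS analyses and listings, and 3.9.4 does not call these criteria PCS. This is at most missing detail.

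**Conclusion.** The point holds as a defect in a stated rule. Followed literally, SAP 3.9.4 with SAP 6.1 counts as emergent both persistent pre-existing positives and first positives after treatment has ended. The second group can come only from subjects who do not enter the extension.

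The effect is to raise the descriptive percentage in each arm. The documents give neither baseline positivity nor movement-disorder rates, so the amount cannot be estimated. It is zero if nobody is positive at baseline or first positive at Visit 7. The figures in the working show only what assumed inputs would produce.

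A reader might go further and infer that the comparison between arms is biased. The documents do not show this. With balanced baselines, equal persistence and equal Visit 7 attendance, the difference in percentage points changes little. The ratio would be pulled towards 1, but no ratio or test is planned for these counts. Persistence and attendance could differ by arm, but nothing in the documents says that they do. The efficacy analyses are untouched.

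Weight, QTc and supine vital-sign PCS counts are also measured at Visit 7 and have no stated period limit. That is a separate, minor point.

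**What to change.** In SAP 3.9.4, for each of the three outcomes:

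- Denominator: Safety Population subjects who do not meet the criterion at baseline and have at least one post-baseline rating in the double-blind period.
- Numerator: those of them who meet the criterion during that period.
- Report Visit 7 separately.

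For the AIMS, BARS and SAS shifts named in Protocol 14.6, either present them, for which these baseline-negative counts may serve, or record the change in SAP 5.

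The cost is a few sentences and minor programming on data already collected, since the scales are rated predose on Day 1. The denominator becomes slightly smaller: with an assumed 5% positive at baseline it is 130 × 0.95 = 123.5 per arm. Subjects positive at baseline leave this count, but their scores remain in the by-visit summaries and the listings.
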